## 5.3.2 Exclusion Criteria

- Current or planned pregnancy or lactation
- Unwillingness to discontinue sirolimus
- Change in the dose or use of sirolimus within the past month
- Inability to perform spirometry
- Other serious illness that would impact the outcome of the study
- Current lung transplant
- Current cigarette smoking
- Required use of ketoconazole, itraconazole, clarithromycin, or rifampin during the 2 months of the study.
- Unwillingness to avoid grapefruit juice or St. Johns Wort during the study.
- Planned surgery during the 2 months of the study..

\*Children are excluded because LAM does not affect children

\*\*Definite or Probable LAM is defined by the ERS LAM guidelines modified by addition of VEGF-D criteria as defined by the MILES Trail

Definite LAM:

1) Characteristic or compatible lung HRCT, and lung biopsy fitting the pathological criteria for LAM; or 2) Characteristic lung HRCT and any of the following: angiomyolipoma (kidney); thoracic or abdominal chylous effusion; lymphangioleiomyoma or lymph-node involved by LAM; and definite or probable TSC.

Probable LAM

1) Characteristic HRCT and compatible clinical history; or

2) Compatible HRCT and any of the following: angiomyolipoma (kidney); thoracic or abdominal chylous effusion; or VEGF-D >800 pg/ml at any time in the past.

## 5.4 Visit Schedule

**The Baseline Visit** will begin with signing the informed consent. A history and physical examination, post-bronchodilator spirometry, 6 minute walk test distance, and blood samples will be obtained. Questionnaires will be completed and the patient will be randomized to imatinib mesylate, at an oral dose of 400 mg once daily, or placebo stratified on whether sirolimus has been used in the last month. A sirolimus level and VEGF-D level will be measured.

A 1 week trough sirolimus level and telephone call will be obtained on all subjects entering the study on sirolimus therapy.

**1 Month Visit-** Post-bronchodilator spirometry, 6 minute walk test distance, and blood samples will be obtained. Questionnaires will be completed. Sirolimus will be discontinued if used at baseline.

**2 Month Visit/ End of study-** Post-bronchodilator spirometry, 6 minute walk test distance, and blood samples will be obtained. Questionnaires will be completed. A sirolimus level will be obtained to assure drug cessation. The participant is returned to LAM therapy of their choice.

[figure not shown]

Figure 1. Study Schedule, Stratification and Randomization

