## Table 1. Procedures by Visit

			······································						
	Baseline (V1)	1 Month (V2)	2 Months (V3)						
1.Informed Consent	Х								
2.Pulmonary Function Testing	Х	Х	Х						
3.Six Minute Walk Test	Х	Х	Х						
4.Blood Sample Collection*	Х	Х	Х						
5.Urine Sample Collection*	Х	Х	Х						
6.Participant Questionnaires	Х	Χ	Х						

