## 6.1.3 Imatinib side effects

The most common side effects of imatinib include nausea, diarrhea, headaches, leg cramps, fluid retention, visual disturbances, rash, weight gain, and reduced number of blood cells (any cell line can be affected). Imatinib is an immune suppressant and increases risks of common and uncommon infections.

Severe systolic congestive heart failure is an uncommon but recognized side effect of imatinib and mice treated with large doses of imatinib show toxic damage to myocardiocytes. Hypoxemia has been noted in one individual with LAM.

Since imatinib is mainly metabolised via the liver enzyme CYP3A4, substances such as ketoconazole, itraconazole, clarithromycin, and grapefruit juice can increase the plasma concentration of the drug. Conversely, CYP3A4 inducers like rifampin and St. John's Wort reduce the drug's activity. These medications will be prohibited during the study. A known interaction between imatinib and sirolimus in which sirolimus levels rise will be monitored during the study.

Imatinib also acts as an inhibitor of CYP3A4, 2C9 and 2D6, increasing the plasma concentrations of simvastatin, cyclosporin, pimozide, warfarin, and metoprolol. Imatinib also reduces plasma levels of levothyroxin via an unknown mechanism. INR, Cholesterol, T4, and TSH will be measured during the study for all individuals.

An imatinib dose reduction to 200 mg daily will be permitted should a participant experience persistent side effects.

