## 6.3 Adverse Events

An adverse event (AE) is any untoward medical occurrence in a study subject. This may include symptom(s), illness, clinically significant abnormal laboratory value or change in value, or worsening in a subject during a clinical study. Since one of the specific aims of the study is to establish the safety of imatinib in LAM affected individuals, it is the goal of the investigators to capture every AE.

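### The only scheduled physical examination is at baseline, and no visit schedules body weight or an oedema check, although the protocol lists weight gain, fluid retention and heart failure as imatinib effects

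*Combined protocol and SAP*

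**What the plan says.** Section 5.4 gives the content of three visits. At baseline, "A history and physical examination, post-bronchodilator spirometry, 6 minute walk test distance, and blood samples will be obtained". The 1 month entry covers spirometry, a walk test and blood, and ends "Questionnaires will be completed. Sirolimus will be discontinued if used at baseline". The 2 month entry has the same tests and then "Questionnaires will be completed. A sirolimus level will be obtained to assure drug cessation", followed by the return to LAM therapy. Neither on-treatment entry names an examination.

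"Table 1. Procedures by Visit" has six rows: consent, lung function, walk test, blood, urine and questionnaires. It has no row for examination, weight or vital signs at any visit. Section 5.5, which describes the study examinations, adds none of these.

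Section 6.1.3 states: "The most common side effects of imatinib include nausea, diarrhea, headaches, leg cramps, fluid retention, visual disturbances, rash, weight gain", together with reduced blood cell counts. It adds that "Severe systolic congestive heart failure is an uncommon but recognized side effect of imatinib". Safety of imatinib is the third aim in Section 3.2, Section 4.6 describes the trial as designed mainly for safety, and Section 6.3 says "it is the goal of the investigators to capture every AE".

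**The concern.** Weight gain, oedema and early heart failure show as change from baseline on weighing and examination. If neither is scheduled during treatment, the trial has no uniform record of them for comparing imatinib with placebo.

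This matters more than usual here for two reasons. Section 6.3.1 rules out a statistical plan for safety because numbers and observation time are too small, and relies on reporting every adverse event. The listing is therefore the main safety output, and it is only as good as the way events are found. Second, participants on sirolimus stop it at the 1 month visit, and Section 2.1 reports rapid loss of lung function after stopping in an earlier trial. In month 2, breathlessness or falling lung function could reflect either LAM or fluid overload. Section 6.3.1 asks for attribution to drug where it can be determined, and that is harder without weight or oedema findings.

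**Working it through.** The plan states no figure on this point, so there is none to reproduce. The check sets the scheduled assessments beside the listed effects.

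**Count of scheduled assessments**

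| Assessment | Section 5.4 text | Table 1 | On-treatment visits (months 1 and 2) |
|---|---|---|---|
| Physical examination | 1 of 3 visits | 0 of 3 | 0 of 2 |
| Body weight, by name | 0 of 3 | 0 of 3 | 0 of 2 |
| Oedema check, by name | 0 of 3 | 0 of 3 | 0 of 2 |

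With 20 participants and two on-treatment visits, at most 20 × 2 = 40 participant-visits have no examination specified. This counts what the plan omits to require. It does not estimate missed events.

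**Other routes by which these effects could be found**

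- *Solicited reports.* Section 6 has participants asked about adverse events at each visit. Sections 5.5.3 and 6.4 add three coordinator calls.
- *Investigator observation.* Section 6 also records events that investigators observe. With no examination scheduled on treatment, such observation is incidental.
- *Symptom-triggered evaluation.* Section 6.4 calls for evaluation when symptoms worsen, but does not say what it contains.
- *Objective tests.* Sections 5.5.1, 5.5.2 and 6.4 give blood counts, a metabolic panel, urinalysis, spirometry, lung volumes, diffusion capacity, walk distance with oximetry, and a Borg score. Fluid overload could affect some of these. So could LAM itself, in a population selected for impaired lung function.

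**Consistency with the plan's own approach.** Section 6.1.3 also names lowered blood counts and interactions affecting warfarin, simvastatin and levothyroxine. For these the plan schedules counts, INR, cholesterol, T4 and TSH at baseline, day 28 and day 56. Weight and fluid status are named in the same section but have no matching scheduled measurement.

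**What the change would yield.** Weight at three visits gives up to 20 × 3 = 60 values. With 10 per arm (Section 6 prepares 10 sets of each treatment), each arm would have up to 10 paired changes at day 28 and 10 at day 56, assuming no dropout. Measuring only at months 1 and 2 would not secure a paired change, because no baseline weight is named either.

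**The case against.** The best reply is that silence proves little here. The visit text in Section 5.4 is not exhaustive: it leaves out urine, lung volumes and diffusion capacity, all of which are required elsewhere. Table 1 leaves out the baseline examination and the 1 week sirolimus level. The schedule figure is not shown in the text available, and the adverse event forms and Manual of Operations are separate documents. Sites may well weigh participants for lung function testing. This stands in part. The documents show that these measurements are not specified; they do not show that sites will not make them. But urine, lung volumes and diffusion capacity are each picked up in another section, and an on-treatment examination and body weight are not.

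A reader might also infer that safety for these effects rests on self-report alone, or that they are never measured. The documents do not support that. Events are actively asked about, investigator observations are recorded, worsening symptoms are evaluated, and objective though non-specific tests are done at every visit. Nor should one infer that a baseline weight is taken and then not followed up: an examination is scheduled at baseline, but weight is not named.

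It is also fair to say that a scheduled examination would not alter the rule ending participation after symptom deterioration or a 10% decline in FEV1 or FVC, which applies whatever the cause. Sirolimus users in both arms stop it, so the placebo comparison remains. The gain is in describing and attributing events. Finally, about 10 per arm cannot say much about an uncommon event such as heart failure. That limits what the data can show, but weight gain and fluid retention are listed as common.

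**Conclusion.** The point holds as a gap in safety ascertainment. As written, the plan schedules no direct measurement of weight or oedema at any named time and no examination at either on-treatment visit, so it cannot be relied on to produce comparable data by arm for two effects it calls common and one it calls recognised. Section 5.4 and Table 1 also disagree on whether there is a baseline examination.

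This rests on the protocol text available and assumes that no separate form or manual already requires these measurements. No number of missed events can be derived, and none is claimed. The VEGF-D analysis, the significance level and the sample size are untouched. The change is worth making because it serves a stated aim at little cost, and measurements not taken at the visits cannot be recovered later.

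**What to change.** 1. Add a physical examination row to Table 1 and reconcile it with Section 5.4, baseline included.
2. Record body weight at all three visits, baseline included, in Section 5.4 and Table 1.
3. Add a brief examination including oedema at the 1 month and 2 month visits, and record oedema status at the baseline examination so that a later finding can be called new.
4. In Section 6.3.1 or Section 7, state that weight change from baseline and new oedema will be reported by arm at day 28 and day 56, descriptively and without testing, alongside the adverse event listing.

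If another study document already requires any of these, a cross-reference is enough for that item. The cost is a few minutes at visits already attended and a few case report form fields, with no added visit, sample or staff. The change adds measurement only and sets no dose, stopping or treatment rule.

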## Table 1. Procedures by Visit

			······································						
	Baseline (V1)	1 Month (V2)	2 Months (V3)						
1.Informed Consent	Х								
2.Pulmonary Function Testing	Х	Х	Х						
3.Six Minute Walk Test	Х	Х	Х						
4.Blood Sample Collection*	Х	Х	Х						
5.Urine Sample Collection*	Х	Х	Х						
6.Participant Questionnaires	Х	Χ	Х						

## \*Table 2. Sample Collection and Usage

Collection	Volume	Sample	Time(s)*	Planned assays
Blood each visit	30ml	Plasma	0, 1, 2	Cholesterol, CMP
				Sirolimus level, TSH,
				T4, VEGF-D level
	7 ml	Plasma	1 week in patients on	Sirolimus level
			sirolimus at baseline	
	5ml	EDTA	0, 1, 2	CBC
	10ml	Paxgene DNA	0	DNA
	10ml	Paxgene RNA	0, 2	Blood mononuclear cell
				RNA
Urine each visit	10ml	Urine	0, 1, 2	Urinalysis, Pregnancy
				Test

\*Time 0= Baseline, 1=1month, 2=2 months

## 5.5 Study Examinations 5.5.1 Blood and Urine Samples

These are collected at each study visit.

**Safety:** Universal and Occupational Safety and Health (OSHA) and all institutional-specific (such as bloodborne pathogen training) precautions and training requirements should be followed when processing blood and urine. For more detailed safety information see (http://www.osha.gov/SLTC/biologicalagents/index.html).

Urinalysis, pregnancy test, CBC, TSH, T4, Cholesterol, INR and CMP are performed on samples from each visit at the University Laboratories at MUSC and Columbia to look for adverse events and assure patient health and safety during the study. Trough Sirolimus level is performed on a sample from each visit to verify Sirolimus treated vs. naïve at baseline and that sirolimus was stopped in previous sirolimus receivers at the 1 month visit. This may require participants to take sirolimus at a time of the day that corresponds to anticipated study visit time. VEGF-D levels are performed at each visit to test efficacy of imatinib.

All tests except the VEGF-D will be performed in the clinical laboratory of the institution where the patient is seen (MUSC or Columbia University) and will be performed per standard protocol in these trained and certified laboratories. The costs of laboratory analysis are provided for in the study budget.

## 5.5.2 Pulmonary Function Testing and Exercise Tests

These are performed at each study visit.

Comprehensive lung function testing is obtained at each visit in this study. Baseline spirometry is obtained by following ATS guidelines. Post bronchodilator spirometry is obtained with an aggressive protocol of 4 puffs of albuterol and 4 puffs of ipratroprium to allow an optimal assessment. Lung volumes are obtained by plethysmography and diffusion capacity by the single breath method.

A 6MWT is performed at each of the 3 study visits. The 6MWT is performed without supplemental oxygen by methodology of the ATS Standards. Desaturation less than 80% has been associated with some adverse events and will be used to stop the test and measure the distance should that event occur. Oxygen saturation is determined throughout the entire test. A 10 point Borg dyspnea scale is obtained at rest and at the end of the 6MWT.

## 5.5.3 Questionnaires

Multiple questionnaires will be collected at each study visit as delineated in 4.6 above and seen in attachments to this study.

## St. George's Respiratory Questionnaire (SGRQ)

This biomarker for COPD quantifies a patient reported outcome.

## Modified Medical Research Council (MRC) Dyspnea Scale

Dyspnea is an important biomarker of disease severity and risk of death.

## **Functional Assessment Inventory**

The FAI is widely used to judge an individual's productive activity in 7 domains.

## EQ-5D Health Questionnaire

## 5.5.3 Interim phone calls

A study coordinator will call each participant by phone at 1 week +/- 3 days and 2 weeks +/- 3 days after the baseline visit and again 2 weeks +/- 3 days after the 1 month visit. Phone calls will serve as an opportunity to touch base, inquire about any side effects or adverse events, encourage adherence and confirm the next visit. Completion and results of the phone call will be documented in REDCap.

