## 5. STUDY DESIGN AND PROCEDURES

## 5.1 Overview

The proposed study design is a prospective, multicenter, randomized, stratified, double blind, placebocontrolled, proof of principal trial to examine the effect of imatinib mesylate on intrasubject VEGF-D, a biomarker associated with LAM disease activity.

The study is designed as a 3 visit study including baseline, 1 month, and 2 month visits. Since most patients with impaired lung function who would be eligible for this study are already on sirolimus, the proposed study would simultaneously address three issues: 1) provide a biomarker rich proof of principle study of imatinib mesylate in LAM, 2) determine if imatinib mesylate is safe when added to sirolimus, and 3) determine if imatinib mesylate controls vascular endothelial growth factor-D (VEGF-D) once sirolimus is removed. Small numbers of individuals are not on sirolimus; however, this proposal would not exclude them to define if there is a treatment response signal to imatinib mesylate alone. A stratified randomization strategy will differentially enroll participants on or off rapamycin at baseline.

At the conclusion of the study, participants will be returned to clinically available LAM therapy chosen with their treating physician. Imatinib will not be available through the investigators after participation in this study.

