## 6.3.1 Procedures for Adverse Events

Event, date of onset, severity, duration, and relationship to sirolimus or imatinb (if it can be determined) will be recorded on the study AE forms. All adverse events will be followed until they are adequately resolved or stabilized, or for 1 month following study completion, whichever comes first.

If an adverse event occurs during a study visit the study coordinator should first insure the participant receives any needed medical attention. If the study coordinator is notified by phone, the coordinator should confirm that the participant has received medical attention. The study coordinator should then notify the site Principal Investigator and complete the Adverse Event Form within seven days of learning of the event. Study coordinators will comply with local regulations and policies when notifying the institutional IRB.

The following general definitions for rating severity should be used for this study:

**Mild:** Awareness of signs or symptoms, but easily tolerated and transient; causing no loss of time from normal activities; symptoms would not require medication or a medical treatment; signs and symptoms are transient.

**Moderate:** Marked symptoms and discomfort severe enough to cause moderate interference with the subject's usual activities. Symptomatic treatment is possible.

**Severe:** Incapacitating with inability to do work or usual activities; signs and symptoms may be of systemic nature or require medical intervention and/or treatment. Hospitalization may be required or prolonged.

The relationship of an AE or SAE to the underlying disease or to the procedure will be attributed using the following definitions:

Not Related: There is no evidence that the event has a relationship to the drug(s).

**Possibly Related**: The event has a timely relationship to the drug(s) used. However, a potential alternative etiology may be responsible for the adverse event.

**Probably Related**: The event has a timely relationship to the drug(s) used and the causative relationship can clearly be established. No potential alternative etiology is apparent.

The number of subjects and observation time in this pilot study is insufficient to develop a composite index or statistical plan for the evaluation of safety endpoints for this study. Therefore, all adverse events, their timing, severity, and attribution will be reported in study reports.

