## 6.4 Measures to Protect the Participant

All participants will have laboratory monitoring of CBC, T4, TSH, Cholesterol, INR, Sirolimus level and complete metabolic panel (CMP) at baseline, 28 days, and 56 days. Side effects may receive imatinib dose reduction to 200 mg daily if persistent. Study withdrawal for side effects is permitted. All side effects will be graded and followed. Side effects suggestive of an infection will prompt cessation of subsequent doses of rapamycin and imatinib mesylate/placebo for 1 week until such symptoms are improved. Any worsening of symptoms would prompt evaluation. Decline in FEV1 or FVC of 10% would prompt end of study, study unblinding, and transition to usual clinical care. A study

coordinator will call each participant to check on how they are doing 1 week +/- 3 days and 2 weeks +/- 3 days after the baseline visit and 2 weeks +/- 3 days after the 1 month study visits.

Study related injuries are addressed in the MUSC Statements of the informed consent form. In the event of a study related injury, the participant should go immediately to the emergency room of the Medical University Hospital, or in case of an emergency go to the nearest hospital, and tell the physician on call that they are in a research study. The doctor should call the study doctor to make arrangements for treatment. If the study sponsor does not pay for treatment, the Medical University Hospital and the physicians who render treatment will bill the participant's insurance. If the insurance company denies coverage or insurance is not available, the participant will be responsible for payment of all services rendered.

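### Adverse events are asked about less often in month 2 than in month 1, and first asked about a week later after sirolimus stops than after study drug starts, so brief events on imatinib alone can be under-recorded

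*Combined protocol and SAP*

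**What the plan says.** The call schedule appears twice, and the two statements agree. Interim phone calls (5.5.3) gives every participant a coordinator call one week into the study, with further calls "2 weeks +/- 3 days after the baseline visit and again 2 weeks +/- 3 days after the 1 month visit". Section 6.4 repeats it: "coordinator will call each participant to check on how they are doing 1 week +/- 3 days and 2 weeks", with the last call again placed 2 weeks after the 1 month visit ("days after the baseline visit and 2 weeks +/- 3 days after the 1 month study visits"). One purpose of the calls is to "inquire about any side effects or adverse events". Section 6 adds that participants are asked about adverse events at every visit and are told at the outset to report any adverse change themselves.

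Section 5.4 stops sirolimus at the 1 month visit in those taking it at baseline. It describes the 1-week call, together with a trough level, only for those entering on sirolimus, whereas 5.5.3 and 6.4 give it to everyone.

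On safety, 2.3 and 3.1 state the hypothesis and primary aim as equivalence of imatinib to sirolimus in short-term efficacy and safety. Section 5.1 also sets out to "determine if imatinib mesylate is safe when added to sirolimus". Section 6.3 aims at complete capture of adverse events. Section 6.3.1 declines a statistical safety plan and says instead that "all adverse events, their timing, severity, and attribution will be reported in study reports".

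**The concern.** For the expected majority on sirolimus, the two months are different treatments: study drug plus sirolimus, then study drug alone. Month 1 has one more scheduled inquiry than month 2, and the extra one falls early. The week after a treatment change is covered by a call when study drug starts, but not when sirolimus stops.

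This matters because the descriptive listing is the whole safety result. In the sirolimus-using stratum, sirolimus without imatinib occurs only in the placebo arm in month 1, and imatinib without sirolimus only in the imatinib arm in month 2. A reading of the equivalence aim on safety within that stratum must therefore set a month with three inquiries against a month with two. Any under-recording would lower the count for imatinib alone, which is the direction that favours the drug under study.

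**Working it through.** The documents give no contact count, event rate or safety power, so there is no figure of the plan's own to reproduce. The check counts scheduled inquiries and then asks how much the difference could matter.

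**Inputs from the documents**
- Visits at baseline, day 28 and day 56 (6.4), with adverse events asked about at each (section 6).
- Calls at 1 and 2 weeks after baseline and at 2 weeks after the 1 month visit, each +/- 3 days (5.5.3, 6.4).
- Sirolimus stopped at the 1 month visit (5.4).

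**Count of inquiries after treatment starts** (the baseline inquiry is left out)
- Month 1: days 7, 14 and 28. Three contacts, gaps of 7, 7 and 14 days.
- Month 2: days 42 and 56. Two contacts, gaps of 14 and 14 days.
- Ratio of contacts: 2/3.
- First contact after study drug starts: 7 +/- 3, so days 4-10.
- First contact after sirolimus stops: 14 +/- 3, so 11-17 days later (study days 39-45).
- If 5.4 governs and only sirolimus users receive the 1-week call, sirolimus-naive participants have two contacts in each month. For sirolimus users the count is three against two on either reading.

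**Mean time from event to next inquiry**, for events spread evenly over the month: sum of gap²/2, divided by 28.
- Month 1: (24.5 + 24.5 + 98)/28 = 5.25 days.
- Month 2: (98 + 98)/28 = 7.0 days.

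**Sensitivity model (assumed, not from the documents).** Events occur at a constant rate, and the chance that an event is reported at the next contact halves every h days. With k = ln 2/h, the captured share over a month is the sum over gaps of (1 − exp(−k·gap))/k, divided by 28. Spontaneous reports are excluded.

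| Assumed h (days) | Month 1 | Month 2 | Ratio |
|---|---|---|---|
| 1 | 0.154 | 0.103 | 0.67 |
| 3.5 | 0.440 | 0.338 | 0.77 |
| 7 | 0.631 | 0.541 | 0.86 |
| 14 | 0.783 | 0.721 | 0.92 |
| 28 | 0.882 | 0.845 | 0.96 |
| 90 | 0.961 | 0.948 | 0.99 |

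Worked case, h = 7: a 7-day gap captures (1 − 0.5)/ln 2 = 0.721 of its events, and a 14-day gap captures (1 − 0.25)/(2 ln 2) = 0.541. Half of month 1 lies in 7-day gaps, so month 1 is (0.721 + 0.541)/2 = 0.631. Month 2 is 0.541.

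**First 14 days after each treatment change**, same model: 72% against 54% (h = 7), 85% against 72% (h = 14), and 92% against 85% (h = 28). The whole difference sits in this fortnight. The second fortnight of each month is a single 14-day gap in both.

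**With a week-1 call added in month 2**, the gaps are 7, 7 and 14 days in both months, and the ratio is 1.00 at every half-life.

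**The case against.** A reader might infer that the withdrawal month looks safer by construction. The documents do not support that. Each call and visit can still pick up events from the whole interval since the last contact, and spontaneous reporting runs throughout, so fewer prompts need not mean fewer recorded events. If half of all events were reported spontaneously (assumed), the whole-month gaps of 9.0, 6.2 and 3.7 percentage points for h = 7, 14 and 28 would halve to about 4.5, 3.1 and 1.8. Serious or persistent events should be little affected. The observed difference also depends on true event rates in each month, which are not given.

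A reader might also infer that the question of safety when imatinib is added to sirolimus is biased. It is not. Imatinib versus placebo among sirolimus users in month 1 answers it, with identical contacts in both arms. Tolerance of withdrawal likewise has a concurrent placebo group in month 2.

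Nor does the rapid deterioration described in 2.1 support the mechanism. That was a progressive fall in lung function, which is measured here at the 2 month visit, not a passing event lost to recall.

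The early call has a rationale too. Section 5.4 pairs it with the sirolimus trough level, and the interaction monitoring in 5.6 and 6.1.3 gives a reason for an early contact that ends when sirolimus stops.

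The strongest objection is that no month 1 versus month 2 safety contrast is planned. That is true as regards tests, but it does not dispose of the point. In the sirolimus-using stratum the equivalence aim in 2.3 and 3.1 has no same-month comparison of the two drugs given separately. Sirolimus-naive participants are expected to be few (5.1), and comparing them with sirolimus users would cross strata and so not be randomised.

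**Conclusion.** The point holds in a limited form. Scheduled solicitation is two contacts against three for participants entering on sirolimus, and the first inquiry after sirolimus stops comes a week later than the first after study drug starts. Brief or mild events soon after withdrawal are the ones at risk.

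The size cannot be fixed from the documents. Under the assumed half-lives of 7 to 28 days, solicited capture in month 2 is 0.86 to 0.96 of that in month 1. The ratio falls to about two thirds if recall fades within a day or so, and is near 1 if recall is long. For scale, with 20 true events in each month (assumed) and no spontaneous reporting, the gaps of 9.0 to 3.7 points mean about 1.8 to 0.7 fewer recorded events in month 2 (20 × 0.090 and 20 × 0.037).

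No efficacy analysis and no within-month comparison of imatinib with placebo is affected. What is affected is any description of imatinib alone against sirolimus alone, or of month 2 against month 1.

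**What to change.** - In 5.5.3 (Interim phone calls) and 6.4, add a call 1 week +/- 3 days after the 1 month visit with the same adverse event questions, so that both months have contacts at 1, 2 and 4 weeks.
- In 6.3.1, state that adverse events will be reported by arm and stratum separately for Day 0-28 and Day 28-56.
- State there that any between-month comparison is descriptive. Equal calls do not remove period and order effects, such as time since imatinib started, dose reductions and earlier withdrawals.
- Reconcile 5.4, which gives the 1-week call to sirolimus users, with 5.5.3 and 6.4, which give it to each participant.

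The cost is at most 20 extra coordinator calls (one for each of 20 participants) and a few sentences of text. No visit or sample is added. If the call is not added, the reporting by month and the stated limitation are still needed, with the unequal number of inquiries given beside the tables.
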